Appendix C: Clavien-Dindo Classification for Surgical Complications

The Clavien-Dindo Classification of Surgical Complications

Full Scale		Contracted Form	
Grades	Definition	Grades	Definition
Grade I:	Any deviation from the normal postoperative course without the need for pharmacological treatment or surgical, endoscopic and radiological interventions. Allowed therapeutic regimens are: drugs as antiemetics, antipyretics, analgesics, diuretics and electrolytes and physiotherapy. This grade also includes wound infections opened at the bedside.	Grade I:	Same as for Full Scale
Grade II:	Requiring pharmacological treatment with drugs other than such allowed for grade I complications. Blood transfusions and total parenteral nutrition are also included.	Grade II:	Same as for Full Scale
Grade III:	Requiring surgical, endoscopic or radiological intervention	Grade III:	Grades IIIa & IIIb
Grade III-a:	intervention not under general anesthesia		
Grade III-b:	intervention under general anesthesia		
Grade IV:	Life-threatening complication (including CNS complications)‡ requiring IC/ICU-management	Grade IV:	Grades IVa & IVb
Grade IV-a:	single organ dysfunction (including dialysis)		
Grade IV-b:	multi organ dysfunction		
Grade V:	Death of a patient	Grade V:	Same as for Full Scale
Suffix 'd':	If the patients suffers from a complication at the time of discharge, the suffix “d” (for ‘disability’) is added to the respective grade of complication. This label indicates the need for a follow-up to fully evaluate the complication.		

‡ brain hemorrhage, ischemic stroke, subarachnoidal bleeding, but excluding transient ischemic attacks (TIA); IC: Intermediate care; ICU: Intensive care unit.

Appendix D: Examples of Grading Using Clavien-Dindo Classification

Grades	Organ System	Examples
Grade I	Cardiac	Atrial fibrillation converting after correction of K ⁺ -level
	Respiratory	Atelectasis requiring physiotherapy
	Neurological	Transient confusion not requiring therapy
	Gastrointestinal	Noninfectious diarrhea
	Renal	Transient elevation of serum creatinine
	Other	Wound infection treated by opening of the wound at the bedside
Grade II	Cardiac	Tachyarrhythmia requiring β -receptor antagonists for heart rate control
	Respiratory	Pneumonia treated with antibiotics on the ward
	Neurological	TIA requiring treatment with anticoagulants
	Gastrointestinal	Infectious diarrhea requiring antibiotics
	Renal	Urinary tract infection requiring antibiotics
	Other	Same as for I but followed by treatment with antibiotics because of additional phlegmonous infection
Grade IIIa	Cardiac	Bradycardia requiring pacemaker implantation in local anesthesia
	Neurological	See grade IV
	Gastrointestinal	Biloma after liver resection requiring percutaneous drainage
	Renal	Stenosis of the ureter after kidney transplantation treated by stenting
	Other	Closure of dehiscent noninfected wound in the OR under local anesthesia
Grade IIIb	Cardiac	Cardiac tamponade after thoracic surgery requiring fenestration
	Respiratory	Bronchopleural fistulas after thoracic surgery requiring surgical closure
	Neurological	See grade IV
	Gastrointestinal	Anastomotic leakage after descenderectomy requiring relaparotomy
	Renal	Stenosis of the ureter after kidney transplantation treated by surgery
Grade IVa	Other	Wound infection leading to evisceration of small bowel
	Cardiac	Heart failure leading to low-output syndrome
	Respiratory	Lung failure requiring intubation
	Neurological	Ischemic stroke/brain hemorrhage
	Gastrointestinal	Necrotizing pancreatitis
Grade IVb	Renal	Renal insufficiency requiring dialysis
	Cardiac	Same as for IVa but in combination with renal failure
	Respiratory	Same as for IVa but in combination with renal failure
	Gastrointestinal	Same as for IVa but in combination with hemodynamic instability
	Neurological	Ischemic stroke/brain hemorrhage with respiratory failure
Suffix "d"	Renal	Same as for IVa but in combination with hemodynamic instability
	Cardiac	Cardiac insufficiency after myocardial infarction (IVa-d)
	Respiratory	Dyspnea after pneumonectomy for severe bleeding after chest tube placement (IIIb-d)
	Gastrointestinal	Residual fecal incontinence after abscess following descenderectomy with surgical evacuation. (IIIb-d)
	Neurological	Stroke with sensorimotor hemisyndrome (IVa-d)
	Renal	Residual renal insufficiency after sepsis with multiorgan dysfunction (IVb-d)
	Other	Hoarseness after thyroid surgery (I-d)

TIA, transient ischemic attack; OR, operating room.

Appendix E: Wound Healing Assessment - GTSD Training Manual- Pages 246-248

General Thoracic Surgery Database
V2.41 Training Manual
 September 4, 2020

Diagnosis of empyema should be confirmed by thoracentesis or drain placement: frank pus or cloudy fluid may be aspirated from the pleural space. The fluid typically has leukocytosis, low pH (<7.2), low glucose (<60 mg/dl) high LDH, elevated protein and may contain infectious organisms.

Every empyema is an organ space infection. It is not necessary to capture both empyema and SSI. Capture empyema as it is more specific than SSI.

ParentLongName: Postoperative Events Occurred
 ParentShortName: POEvents
 ParentValue: = "Yes"
 ParentHarvestCodes: 1

Harvest Codes:

Code:	Value:
1	Yes
2	No

SeqNo: 3740
Long Name: Surgical Site Infection
Short Name: SurgSiteInfect
Definition: Indicate the extent of surgical site infection if one was present within 30 days of surgery.

Intent/Clarification:

Surgical Site Infection (SSI)

Superficial incisional SSI
 Must meet the following criteria:
 Date of event for infection occurs within 30 days after any NHSN operative procedure (where day 1 = the procedure date) AND involves only skin and subcutaneous tissue of the incision AND patient has at least one of the following:

- a. purulent drainage from the superficial incision.
- b. organisms identified from an aseptically-obtained specimen from the superficial incision or subcutaneous tissue by a culture or non-culture based microbiologic testing method which is performed for purposes of clinical diagnosis or treatment (for example, not Active Surveillance Culture/Testing (ASC/AST).
- c. superficial incision that is deliberately opened by a surgeon, attending physician** or other designee and culture or non-culture based testing is not performed. AND patient has at least one of the following signs or symptoms: pain or tenderness; localized swelling; erythema; or heat.
- d. diagnosis of a superficial incisional SSI by the surgeon or attending physician** or other designee.

There are two specific types of superficial incisional SSIs:

1. Superficial Incisional Primary (SIP) – a superficial incisional SSI that is identified in the primary incision in a patient that has had an operation with one or more incisions (for example, C-section incision or chest incision for CBGB)
2. Superficial Incisional Secondary (SIS) – a superficial incisional SSI that is identified in the secondary incision in a patient that has had an operation with more than one incision (for example, donor site incision for CBGB)

246 | Page

General Thoracic Surgery Database

V2.41 Training Manual

September 4, 2020

An infected burn wound is classified as BURN and is not an SSI.

Deep incisional SSI

Must meet the following criteria:

The date of event for infection occurs within 30 days after the NHSN operative procedure (where day 1 = the procedure date) AND involves deep soft tissues of the incision (for example, fascial and muscle layers) AND patient has at least *one* of the following:

- a. purulent drainage from the deep incision.
- b. a deep incision that spontaneously dehisces, or is deliberately opened or aspirated by a surgeon, attending physician** or other designee AND organism is identified by a culture or non-culture based microbiologic testing method which is performed for purposes of clinical diagnosis or treatment (for example, not Active Surveillance Culture/Testing (ASC/AST) or culture or non-culture based microbiologic testing method is not performed AND patient has at least *one* of the following signs or symptoms: fever (>38°C); localized pain or tenderness. A culture or non-culture based test that has a negative finding does not meet this criterion.
- c. an abscess or other evidence of infection involving the deep incision that is detected on gross anatomical or histopathologic exam, or imaging test.

There are two specific types of deep incisional SSIs:

1. Deep Incisional Primary (DIP) – a deep incisional SSI that is identified in a primary incision in a patient that has had an operation with one or more incisions (for example, C-section incision or chest incision for CBGB)
2. Deep Incisional Secondary (DIS) – a deep incisional SSI that is identified in the secondary incision in a patient that has had an operation with more than one incision (for example, donor site incision for CBGB)

Organ/Space SSI

Must meet the following criteria:

Date of event for infection occurs within 30 days after operative procedure (where day 1 = the procedure date) AND infection involves any part of the body deeper than the fascial/muscle layers, that is opened or manipulated during the operative procedure AND patient has at least *one* of the following:

1. purulent drainage from a drain that is placed into the organ/space (for example, closed suction drainage system, open drain, T-tube drain, CT guided drainage)
2. organisms are identified from fluid or tissue in the organ/space by a culture or non-culture based microbiologic testing method which is performed for purposes of clinical diagnosis or treatment (for example, not Active Surveillance Culture/Testing (ASC/AST).
3. an abscess or other evidence of infection involving the organ/space that is detected on gross anatomical or histopathologic exam, or imaging test evidence suggestive of infection. AND meets at least *one* criterion for a specific organ/space infection of Mediastinitis (see below).

MED-Mediastinitis

Mediastinitis must meet at least *one* of the following criteria:

1. Patient has organism(s) identified from mediastinal tissue or fluid by a culture or non-culture based microbiologic testing method which is performed for purposes of clinical diagnosis or treatment, for example, not Active Surveillance Culture/Testing (ASC/AST)
2. Patient has evidence of mediastinitis on gross anatomic or histopathologic exam.
3. Patient has at least *one* of the following signs or symptoms: fever (>38.0°C), chest pain*, or sternal instability*

And at least *one* of the following:

General Thoracic Surgery Database
 V2.41 Training Manual

September 4, 2020

- . purulent drainage from mediastinal area
 - . mediastinal widening on imaging test
- Patient ≤ 1 year of age has at least *one* of the following signs or symptoms: fever ($>38.0^{\circ}\text{C}$), hypothermia ($<36.0^{\circ}\text{C}$), apnea*, bradycardia*, or sternal instability* And at least *one* of the following:
- purulent drainage from mediastinal area
 - mediastinal widening on imaging test
- * With no other recognized cause

The mediastinal space is the area under the sternum and in front of the vertebral column, containing the heart and its large vessels, trachea, esophagus, thymus, lymph nodes, and other structures and tissues. It is divided into anterior, middle, posterior, and superior regions.

Report mediastinitis (MED) following cardiac surgery that is accompanied by osteomyelitis as SSI-MED rather than SSI-BONE.

CDC, Surgical Site Infection (SSI) Event, January 2018,
<https://www.cdc.gov/nhsn/pdfs/pscmanual/9pscscsicurrent.pdf>

ParentLongName: Postoperative Events Occurred
 ParentShortName: POEvents
 ParentValue: = "Yes"
 ParentHarvestCodes: 1

Harvest Codes:

Code: Value:

- 1 None
- 2 Superficial
- 3 Deep
- 4 Organ space

SeqNo: 3750

Long Name: Sepsis

Short Name: Sepsis

Definition: Indicate whether the patient experienced sepsis (septicemia) requiring positive blood cultures in the postoperative period.

Intent/Clarification: Sepsis is defined as evidence of serious infection accompanied by a deleterious systemic response. In the time period of the first 48 postoperative or post procedural hours, the diagnosis of sepsis requires the presence of a Systemic Inflammatory Response Syndrome (SIRS) resulting from a proven infection (such as bacteremia, fungemia or urinary tract infection). In the time period after the first 48 postoperative or post procedural hours, sepsis may be diagnosed by the presence of a SIRS resulting from suspected or proven infection. During the first 48 hours, a SIRS may result from the stress associated with surgery and/or cardiopulmonary bypass. Thus, the clinical criteria for sepsis during this time period should be more stringent. A systemic inflammatory response syndrome (SIRS) is present when at least two of the following criteria are

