15	DATA HANDLING AND RECORD KEEPING.....	35
15.1	Data Collection and Management Responsibilities	35
15.2	Protocol Deviations.....	36
15.3	Study Closure	36
15.4	Study Records Retention.....	36
16	APPENDICES	37
	Appendix A: ECOG Performance Status.....	37
	Appendix B: Reportable Events	38
	Adverse Event (AE) Definition	38
	Serious Adverse Event (SAE) Definition	38
	Unanticipated Problem 39	
	Suspected Adverse Reaction.....	39
	Expectedness and Attribution	39
	Expectedness 39	
	Attribution 40	
	Adverse Event Monitoring 40	
	Appendix C: Clavien-Dindo Classification for Surgical Complications.....	42
	Appendix D: Examples of Grading Using Clavien-Dindo Classification	43
	Appendix E: Wound Healing Assessment - GTSD Training Manual- Pages 246-248	44
17	LITERATURE REFERENCES.....	47

SCHEMATIC OF STUDY DESIGN

**Pre-Operative Immuno-Modulatory SBRT
(POIMS Trial)
A pilot trial in early stage NSCLC**

PROTOCOL SUMMARY

Title	Pre-Operative Immuno-Modulatory SBRT (POIMS Trial): A pilot trial in early stage NSCLC
Protocol Number	IIT-2020-POIMS-Lung
Phase	Pilot
Design	Single arm pilot trial
Study Duration	
Approximately 5 years
 
 • Enrollment Period – approximately 18 months • Follow up period for adverse events to 36 months after surgery • Follow up period for post-operative surgical complication / wound healing events- 3-6 months after surgery • Follow-up period for disease outcome–36 months after surgery
Study Center	University of Kansas Cancer Center
Objectives	
Primary: Assess the impact of non-ablative SBRT (800 cGy X 3 fractions) on immunomodulation in NSCLC tumor cells
 
Secondary: Assess the impact of non-ablative SBRT (800 cGy X 3 fractions) prior to surgical resection on peri- and post-operative surgical complication rate, wound healing, and disease outcomes.

Number of Participants	10

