Diagnosis and Main Inclusion Criteria	
Inclusion Criteria:
 
 • Stage I-II NSCLC • Adequate diagnostic biopsy tissue to allow pre-SBRT tumor analysis • Candidate for oncologic surgery (lobectomy or sub lobar resection) for the lung cancer • Lesion located peripherally, ≥ 2 cm from bronchial margin, and 1 cm from visceral pleura, with location deemed acceptable by cardio-thoracic surgeon for resection. • Adequate pulmonary function test results 
Exclusion Criteria:
 
 • Prior history of lung/chest wall surgery • Prior chest radiation • Prior immunotherapy • History of autoimmune disease • Currently using immunosuppressive drugs
Study Product(s), Dose, Route, Regimen	SBRT 800 cGy x 3 fractions

Duration of Administration
	
Total: 4-5 days
 
1-2 days - consultation and simulation
 
3 treatment (study intervention) days
 
Study intervention (SBRT) delivery will be scheduled for 3 consecutive days, but may be modified as needed by the treating radiation oncologist.

Interim Monitoring
	
The data safety monitoring committee (DSMC) of The University of Kansas Cancer Center is responsible for monitoring participant safety for this trial.

Statistical Methodology
	
We will summarize peri- and post- operative surgical complication rates as well as tumor control outcomes using descriptive statistics.
 
Peri- and post- operative surgical complication rates will be quantified using the Clavien-Dindo classification of surgical complications ^{1,2}.
 
Wound healing complication rates will be scaled as defined by the General Thoracic Surgery Database. ³

Stopping Rules
	
If a participant experiences one or more of the following events, possibly related to study intervention, study will be suspended pending DSMC review to determine if study should continue.
 
 a. Wound healing delay beyond standard timeframe as deemed by study Cardio-Vascular (CV) surgeons b. Peri operative/post-operative surgical complications beyond acceptable institutional rates as determined by study CV surgeons c. Death from study intervention

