1.3 Risk/Benefit Assessment

1.3.1 KNOWN POTENTIAL RISKS

Immediate Risks	Wound healing problems, increase in peri-operative bleeding, bronchopleural fistula, prolonged air leak, conversion to open procedure, and/or infection.
Other Risks	Inconvenience to participant due to additional study-related visits (in addition to standard of care visits): 1 screening/enrollment visit, 1 simulation visit and 3 SBRT treatments.

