3.2 Secondary Objectives

- Assess the impact of non-ablative SBRT (800 cGy X 3 fractions) prior to surgical resection on peri- and post-operative complication rate, and wound healing.
 - Surgical complications will be assessed using the Clavien-Dindo Classification system. The Clavien-Dindo classification system has been validated and established as an “objective, reproducible” grading classification.¹⁷
 - This classification system uses a grading based on the extent of intervention needed to manage a specific complication. See appendices C and D for examples.
 - Wound healing will be assessed and charted by the study cardio-vascular (CV) surgeons using the General Thoracic Surgery Database with particular references to pages 246-248. See Appendix E.
- Describe loco-regional control, metastasis-free survival, disease-free and overall survival in patients treated on this trial with pre-operative SBRT followed by surgery

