3.4 Secondary Endpoints

What is being measured	Measurement time frame	Measurement Tool

The impact of pre-surgical non-ablative SBRT on peri- and post-operative surgical complication rate
	
From Day of post-SBRT surgery through 6 month (± 2 months) post-operative follow up visit
	
Medical Record Review Clavien-Dindo Classification system

The impact of pre-surgical non-ablative SBRT on wound healing
	
From Day of post-SBRT surgery through 6 month (± 2 months) post-operative follow up visit
	
Medical record review General Thoracic Surgery Database.

Loco-regional control, metastasis-free survival, disease free and overall survival
	
From Day of enrollment through 36 month follow up visit
	
Medical record review

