12 STATISTICAL CONSIDERATIONS

12.1 Description of Statistical Methods

We will summarize peri- and post- operative surgical complication rates as well as tumor control outcomes using descriptive statistics.

Peri- and post- operative surgical complication rates will be quantified using the Clavien-Dindo classification of surgical complications.

Wound healing complication rates will be scaled as defined by the General Thoracic Surgery Database with particular references to pages 246-248.

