12.2 Study Stopping Rules

If a participant experiences one or more of the following events, possibly related to study intervention, study will be suspended pending data safety monitoring committee (DSMC) review to determine if study should continue:

- a. Wound healing delay beyond standard timeframe as deemed by study Cardio-Vascular (CV) surgeons
- b. Peri operative/post-operative surgical complications beyond acceptable institutional rates as determined by study CV surgeons
- c. Death from study intervention

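### The wound-healing rate is scaled on Appendix E pages that record only infection, and their one graded item stops at day 30, while 3.4 follows wound healing to the 6-month (± 2 months) visit

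*Protocol*

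**What the plan says.** Protocol 3.2 states that wound healing will be "assessed and charted by the study cardio-vascular (CV) surgeons using the General Thoracic Surgery Database with particular references to pages 246-248", and refers the reader to Appendix E. Protocol 12.1 turns this into the analysis scale: "Wound healing complication rates will be scaled as defined by the General Thoracic Surgery Database with particular references to pages 246-248". Appendix E carries the title Wound Healing Assessment and prints those manual pages.

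The visible content is the end of an empyema item (yes/no), a full SSI item coded none, superficial, deep or organ space, and the start of a sepsis item. The SSI item is defined as: "Indicate the extent of surgical site infection if one was present within 30 days of surgery". Each of its three positive levels repeats the 30-day limit.

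The time frame for wound healing in 3.4 is "From Day of post-SBRT surgery through 6 month (± 2 months) post-operative follow up visit", and the tools listed there are medical record review and the GTSD, without pages. Sections 9.1.2 and 9.3 schedule a wound healing assessment at discharge, at 1-3 weeks and at 6 months. The Protocol Summary gives a different period: "Follow up period for post-operative surgical complication / wound healing events- 3-6 months after surgery".

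**The concern.** The secondary hypothesis in section 2 includes a claim that the regimen leaves wound healing unaffected. The scale printed for that endpoint measures something narrower: whether a wound or chest infection occurred and, for SSI, how deep it went within 30 days.

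The protocol itself keeps healing and infection apart. Section 1.3.1 lists both among the immediate risks: "Wound healing problems, increase in peri-operative bleeding, bronchopleural fistula, prolonged air leak, conversion to open procedure, and/or infection". Section 12.2 names a category of its own: "Wound healing delay beyond standard timeframe as deemed by study Cardio-Vascular (CV) surgeons". Appendix D gives closure of an uninfected dehisced wound as a Clavien-Dindo IIIa example.

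What is at stake is the meaning of the reported rate. A result of zero on the printed scale could mean no early infection and be read as no healing problem, even if other parts of the trial database recorded one.

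**Working it through.** The protocol states no figure for this endpoint, so there is none to reproduce. The check compares event types and time windows.

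**Event types.** Visible GTSD items: empyema, SSI, sepsis, so 3 items, all infection; items recording healing: 0. This describes the printed excerpt, not the whole database. Dehiscence appears only as one route to a deep incisional SSI (criterion b), which a negative test does not satisfy. The superficial level accepts a surgeon's diagnosis, but it must still be a diagnosis of infection within 30 days.

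| Wound event | SSI code | Reason | Where else it may be held |
|---|---|---|---|
| Infection at any of the three levels, by day 30 | Positive | Meets a printed level | Clavien-Dindo, adverse events |
| Delayed healing without infection | None | Every positive level requires infection | Surgeon's charting, record review, adverse events |
| Deep dehiscence, negative test, no pus, abscess or other evidence of infection | None | Fails criteria a, b and c | Clavien-Dindo (Appendix D, IIIa), record review |
| SSI first arising after day 30 | None | Outside the limit at 3 of 3 positive levels | 6-month assessment, record review, adverse events |

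**Time windows.** Inputs: the 30-day limit (Appendix E), the 6-month visit ± 2 months (3.4), and an assumed month of 30.4 days.

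- Earliest end of the 3.4 window: 4 × 30.4 = 122 days.
- Latest end: 8 × 30.4 = 243 days.
- Part of the window after the SSI limit: 122 − 30 = 92 days to 243 − 30 = 213 days.

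The 6-month wound assessment therefore cannot give a positive SSI code for a new event; it can only record in retrospect one that began by day 30.

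**Weight of one event.** With all 10 planned participants in the denominator, one participant whose only wound event is unscored shifts the rate by 1/10 = 10 percentage points. This shows how coarse the rate is; it does not predict an omission.

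**Follow-up wording.** The summary's period ends between months 3 and 6; the 3.4 window ends between months 4 and 8. An event at month 7 can fall inside the second and lies outside the first.

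**The case against.** The strongest reply is that the protocol does not confine the endpoint to these pages. A particular reference is emphasis, not restriction. The Protocol Summary says only "Wound healing complication rates will be scaled as defined by the General Thoracic Surgery Database", with no pages, and 3.4 adds record review. Surgeons chart healing at three scheduled assessments, and the 6-month one shows an intent to look past day 30. Clavien-Dindo grading has the same 3.4 window, and 11.2 collects all adverse events to 36 months after surgery. The case report forms are customized for the study and are not shown. With 10 participants and descriptive analysis, wound events can be listed case by case.

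Most of this stands, and it limits the point to a conditional one. It does not remove it. The protocol names no other GTSD item, and record review is a source of data rather than a scale. Clavien-Dindo is the tool of a separate endpoint row. The scale is fixed in the protocol itself, so it is not a detail merely left to an analysis plan.

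The documents do not support several stronger readings that a reader might infer:

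- That healing problems go unrecorded. Several other routes may hold them.
- That every wound event after day 30 scores as none. No 30-day limit is printed for empyema or sepsis, and the sepsis item refers to the postoperative period.
- That the healing-delay criterion in 12.2 cannot work. It cites no instrument and rests on the surgeons' judgement.
- That 92 to 213 days measures lost events. It is calendar time.

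**Conclusion.** The mismatch is real but conditional. If the wound-healing rate is scaled on the pages that 3.2 and 12.1 single out, it is an infection rate whose only graded component closes at day 30, reported under a healing label with a window of 4 to 8 months. Non-infected delayed healing, test-negative deep dehiscence without other evidence of infection, and SSI arising after day 30 would receive no positive SSI code.

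This rests on two assumptions: that no other GTSD field is used for the rate, and that the visible excerpt represents the pages cited. The protocol gives no rate of delayed healing, dehiscence or late infection, so the size of any understatement cannot be estimated.

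The importance is minor to moderate: the change should be made, but the endpoint is secondary and no formal test depends on it. The differing follow-up period in the summary is a side matter of alignment and adds no weight to the main point.

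**What to change.** Amend 3.2, 3.4 and 12.1 to report two results:

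1. **Infection outcomes, under that name:** SSI within 30 days, empyema and sepsis. Use the full GTSD definitions, because the excerpt shows only part of the empyema and sepsis items. Do not also count an empyema as an SSI, as Appendix E itself instructs.
2. **Wound-healing complication rate:** the proportion of participants with any surgeon-recorded wound problem, infected or not, through the 3.4 window, each participant counted once. Take it from the three scheduled wound assessments, the planned record review and the wound events graded under Clavien-Dindo. State that it overlaps with the surgical complication endpoint.

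Retitle or annotate Appendix E as covering infection items only. As a minor alignment, reconcile the follow-up period in the Protocol Summary with 3.4.

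The cost is amended wording and no new visits. A small case report form field is needed only if the customized forms lack one. There are two downsides. A surgeon-recorded wound problem is less standardized than the GTSD infection definitions. Events between week 3 and the 6-month visit will depend on record review.
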